The primary analysis will be a between-arm comparison of the change from baseline in global composite cognition score, measured at Burst 2 (approximately month 9) as estimated from the ANCOVA regression model, which also includes adjustment for the stratification factors $Strat_i$ = (sex, age, years of education):

$$Z_{i2} = \beta_0 + \beta_1 Z_{i1} + \beta_2 Arm_i + \beta_3^T Strat_i + e_i.$$

In this model, age and years of education are treated as continuous. The stratification variables are added to assure proper confidence interval width, since randomization included stratification involving these variables (Kahan and Morris 2011). The coefficient β_2 quantifies the difference between treatment arms at Burst 2, adjusted for the baseline Burst 1 composite score measure and stratification variables, and will be fit using linear regression.

A supportive analysis of the primary endpoint will be the adjusted analysis examining the treatment effect on the change from baseline at Burst 2 for each of the three individual task domain scores \bar{Y}_{i2}^d .

Analysis of Secondary Outcomes

We will consider the treatment effect on the individual tasks (symbol search, color shapes and grid memory) in a longitudinal session-level model with the post-baseline session level outcome Y_{ijk}^d ($j>1$) regressed on the baseline average $Y_{i1.}^d$, treatment arm, time since baseline $time_{ij}$, time of day t_{ijk} (continuous covariate 0-24, centered at group average), day of week (i.e work day or day off), season (4 level factor variable: winter, spring, summer, fall), practice effects $g(s_{ijk})$ as a function of s_{ijk} (session number 1-35 as a continuous covariate), and, fatigue (visual

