where b_{ij} is the person level effect (random intercept term) for participant i and Burst j , and e_{ijk} is the residual error term assumed to be mean 0, independent across time and individuals and approximately normally distributed. In this model, response Y_{ijk}^d is modeled as a function of the overall baseline level and the term β_4 summarizes the potential treatment effect on the change over time. Models will be further adjusted for age, gender, APOE4 allele, race, and ethnicity in supportive analyses. The difference in time and underlying cognitive function within a burst is assumed negligible, thus the time and season variables in these models will be determined by the first day of the Burst.

The Color Shapes task has only 7 possible values, so a similar generalized estimating equation (GEE) approach will be taken using the Poisson mean model and robust sandwich variance for the number of incorrect responses (0-6).

Our secondary outcomes also include between arm comparisons of MHD-related dietary intake based on self-report and biomarker measures of intake at 9 months post baseline. Outcome models of between-arm differences in dietary intakes indicative of the MHD as measured by nutritional biomarkers, and self-report at Burst 2 will be conducted in a similar manner to the models specified above for the primary cognitive outcomes: namely, ANCOVA models that adjust for the baseline level, Arm and stratification factors will be fit. Tocopherols and carotenoids plasma biomarkers will be additionally adjusted for cholesterol variables per Gross et al (2003). Longitudinal models considering ASA24 data across the 4 bursts will be fit using similar mixed effects models, simplified to analyze only the Burst level average for the ASA24 dietary intakes (no repeated measures within a burst). Analyses will generally be complete case

analyses for the dietary variables. Energy adjustment will be considered where appropriate. Sensitivity analyses with additional adjustment variables associated with missing, as well as exploratory analyses that examine potentially differences in intervention effect by gender, race, ethnicity and age, will also be considered.

The plasma biomarkers include: total folate, alpha and gamma tocopherol, carotenoids (alpha carotene, beta carotene, zeaxanthin+lutein, beta cryptoxanthin, and vitamin B12), lycopene, and fatty acid profile. Serum sodium is an additional secondary outcome, indicative of hydration.

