Self-reported dietary outcomes indicative of the MHD diet include the DII score, which is derived from the self-reported data as both unadjusted and unadjusted for energy, water, and the following factors chosen because of hypothesized pro- or anti-inflammatory effects and because they were readily available summaries from the ASA24: total calories (KCAL), protein (PROT), total fat (TFAT), solid fats (SOLID_FATS), carbohydrates (CARB), total folate from food (FF), folate from non-food sources (non-FF), vitamin B12, carotenoids: retinol (RET), beta carotene (BCAR), alpha carotene (ACAR), cryptoxanthin (CRYP), lycopene (LYCO), Lutein+zeaxanthin (LZ); alpha tocopherol (ATOC), fatty acids (EPA, DPA, DHA), total fruits (F_TOTAL), green leafy vegetables (V_DRKGR), beans and peas (V_LEGUMES), whole grains (G_WHOLE), cured meats (PF_CUREDMEAT), poultry (PF_POULT), seafood high in n-3 fatty acids (PF_SEAFD_HI), nuts and seeds (PF_NUTSD), cheese (D_CHEESE), and added sugars (ADD_SUGARS).

Exploratory Analyses

Exploratory outcomes include the treatment effect on the two exploratory tasks (Shopping List and Rotation Span), which will be evaluated with similar longitudinal models developed for the three domains that make up the primary composite Z score (namely Models 1 and 2). Shopping List will be modeled with a linear mixed effects model. Due to the concern of departure in the Rotation Span scores from normality (a slight truncation), this domain will be modeled with generalized estimating equation with robust variance estimate.

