For any identified important effects of the diet on cognition, we will explore which of the dietary components were mediating that effect. In particular, for the dietary components that seem to be the most different between arms at Burst 2, we will explore whether the Burst 2 measure (or the change from baseline at Burst 2) are associated with a change in the cognitive outcomes at Burst 2 using models similar to that for the primary analysis of the intervention effect. Supportive analyses may also consider formal mediation analyses or the approaches discussed in Freedman et al. 2010 (i.e., both principal components and Howe's method) as ways to efficiently combine the biomarker and self-reported measures of intake in an analysis of their association with cognitive measures. Exploratory dietary effects also include the treatment effect on HbA1c and self-reported vitamin D and choline. The treatment effect on the inflammatory markers IL6 and CRP will also be considered.

For any significant differences by treatment arm, we will examine whether there was evidence of a differential intervention effect across APOE4 groups. Exploratory analyses that examine

potentially differences in identified intervention effects by gender, race, ethnicity and age, will also be considered.

Exploratory analysis will also examine whether there was weight loss at Burst 2 relative to Burst 1 in a complete case analysis:

$$W_{i2} = \beta_0 + \beta_1 W_{i1} + \beta_2 \text{Arm}_i + \beta_3^T \text{Strat}_i + e_i.$$

and if significant changes in weight are identified, analyses will be considered to identify whether any identified intervention effects were potentially mediated by weight loss.

Handling of Missing Data

Analyses of the primary outcome will be done on an intent-to-treat basis; we will assume the data are missing at random (MAR) and use multiple imputation to impute missing measures. Rubin's rules will be used to calculate the variance of the model parameters for each analysis of interest. For secondary outcomes, approaches to address missing data will also assume MAR and approaches to address missing data will generally employ complete case adjustment methods (Little et al., 2022). For missingness rates >10%, sensitivity analyses may be performed using varying assumptions regarding the missing data model to examine whether study conclusions are robust to these differing assumptions. Further details are provided below.

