For randomized trials, under the MAR assumption and when only the outcome variable is missing, complete case analyses that additionally adjust for all the variables related to the missingness imputation will be consistent and can be the most efficient analysis (Little et al, 2022). Thus for the secondary endpoints, the adjustment approach will be considered. For the repeated measures models of the cognitive outcomes, the proposed adjusted analysis models are as described above (Model 1 and Model 2). For the dietary biomarker and self-reported ASA-24 outcomes, adjustment for baseline demographics (age at Burst 1, gender, race, ethnicity, years of education, MOCA score, indicator for in-person vs telephone MOCA, and interaction between the two MOCA variables, and BMI. Energy adjustment will be considered as appropriate for the dietary component. In particular, parsimonious outcome models that include adjustment of variables when found to be associated with missingness will be considered. Analysis of tocopherols and carotenoids plasma biomarkers will be additionally adjusted for cholesterol variables per Gross et al (2003).

References

Van Buuren, S. (2018). *Flexible imputation of missing data.* CRC press.

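### The longitudinal Color Shapes GEE does not cover dropout that depends on Burst 2 or 3 scores, although the SAP assumes MAR, so its arm effects can be biased if that dependence differs by arm

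*SAP*

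**What the plan says.** **Method.** SAP, Analysis of Secondary Outcomes, models each task at session level over Bursts 2 to 4, "regressed on the baseline average" with arm, time, arm by time and session covariates. Grid Memory and Symbol Search get linear mixed models. Color Shapes gets a similar GEE, "using the Poisson mean model and robust sandwich variance for the number of incorrect responses (0-6". The arm-by-time coefficient "summarizes the potential treatment effect on the change over time".

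**Missing data.** Handling of Missing Data states that for secondary outcomes "approaches to address missing data will also assume MAR and approaches to address missing data will generally employ complete case adjustment methods". Sensitivity analyses above 10% missingness are optional.

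**Justification.** Missing data approach for the secondary outcomes argues consistency on a condition: "under the MAR assumption and when only the outcome variable is missing, complete case analyses that additionally adjust for all the variables related" to missingness. For the repeated cognitive outcomes it adds no further covariates: "the proposed adjusted analysis models are as described above (Model 1 and Model 2".

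**Rotation Span.** Under Exploratory Analyses, "this domain will be modeled with generalized estimating equation with robust variance estimate".

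**The concern.** An unweighted GEE is in general consistent only when missingness depends on the covariates in its mean model. Here those include Burst 1 performance and arm, but not performance at Burst 2 or 3. A participant who does badly at Burst 2 and then leaves is missing at random given the observed data, but the SAP's own condition (adjust for everything related to missingness) is not met.

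The longitudinal arm contrast and the arm-by-time term for one of the three domains are at stake. The SAP uses the individual tasks to decide whether an effect belongs to a specific domain, so bias in one task could be read as a domain finding.

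Arm-differential dropout is conceivable. Protocol Section 5.1 asks the MHD arm for food records three times a month for 18 months and lists no such task for the comparison arm. Retention at Visit 2 was 260/290 = 89.7% (protocol Section 3). Missingness is thus already 10.3%, past the SAP's trigger, but that trigger only permits a sensitivity analysis.

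**Working it through.** **The plan's own figures.** The documents give no figure for the Color Shapes GEE. The nearby power and attrition figures in protocol Section 9.2 reproduce closely (two-sided 5% level assumed):
- 125 per arm, 0.35 SD: Φ(0.35·√(125/2) − 1.96) = Φ(0.81) = 79.0% (stated 80%).
- n=143, i.e. 71.5 per arm: Φ(0.35·√(71.5/2) − 1.96) = Φ(0.13) = 55.3% (stated 54%).
- Attrition: 277 × 0.9 = 249 (stated 250); 277 × 0.8³ = 142 (stated 143).

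**Inputs from the documents.** 290 randomised 1:1; up to 35 sessions per burst; outcomes at 9, 18 and 27 months. Burst-to-burst correlation is about 0.90, with 0.5 also considered. Planned dropout is 10% to Burst 2, then 5% (read as per visit); pessimistic dropout is 20% per visit.

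**Assumed inputs.** Mean 1.3 errors per 6-trial session; between-person SD 0.5 on the log scale; equal dropout rates by arm; session covariates omitted. The odds ratios of dropout per SD of the previous burst's score are also assumed: 2 in both arms for the equal case, and from 2 in the comparison arm only up to 3 versus 1/3 for the arm-differential case.

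**Step 1: burst averages.** Log-link Poisson-mean GEE with baseline, arm, time and arm by time; no true effect; 3,000 runs. Type I error for arm by time:

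| Dropout setting | Independence | Exchangeable |
|---|---|---|
| Same mechanism in both arms, either dropout level | 4.3-6.4% | 5.1-5.7% |
| Arm-differential, planned dropout | 5.2-6.8% | 4.3-6.1% |
| Arm-differential, 20% per visit | 7.8-24.8% | 5.3-6.4% |

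With the same mechanism in both arms, the mean estimate (log rate ratio per year) is at most 0.0015 in size. In the arm-differential settings under independence, bias divided by SE is:
- planned dropout: at most 0.0055/0.0279 = 0.20 (correlation 0.9) and 0.0183/0.0495 = 0.37 (correlation 0.5);
- 20% per visit: up to 0.0433/0.0350 = 1.24 and 0.0641/0.0598 = 1.07.

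**Step 2: session level, as the SAP specifies.** A session-level linear check gives type I error of about 4-6% with equal mechanisms and 5-7.5% at planned arm-differential dropout. At 20% per visit it gives 9-19% under independence and 6-27% under exchangeable. A session-level Poisson version (1,000 runs, 20% per visit) gives:
- correlation 0.5: independence 9-17%, exchangeable 14-21%;
- correlation 0.9: independence 8-13%, exchangeable 6-8%.

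Under session-level exchangeable the bias changes sign.

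**Step 3: why exchangeable over-corrects at session level.** One correlation has to serve for pairs within a burst and pairs across bursts. Approximate figures at burst correlation 0.5:
- Between-person variance: 1.3²(e^0.25 − 1) = 0.480. After baseline adjustment: 0.480 × (1 − 0.25) = 0.360. Cross-burst covariance: 0.480 × (0.5 − 0.25) = 0.120. Session variance: 0.360 + 1.3 = 1.660.
- Session correlation within a burst: 0.360/1.660 = 0.217. Across bursts: 0.120/1.660 = 0.072.
- Pairs within bursts: 3 × 595 = 1,785. Pairs across bursts: 3 × 1,225 = 3,675. Pooled α = (1,785 × 0.217 + 3,675 × 0.072)/5,460 = 0.119.
- Implied correlation of burst means: 35α/(1 + 34α) = 0.83. Actual: 35 × 0.072/(1 + 34 × 0.217) = 0.30.

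The fit therefore leans on earlier bursts far more than the data warrant.

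**Step 4: the mixed models.** SAP Model 1 has an intercept for each person and burst, with variance varying by burst and no stated covariance across bursts. In a linear analogue (20% loss, correlation 0.9, no effect), burst-independent intercepts gave bias of about 0.43 SE on arm by time and 0.44 SE on the 27-month contrast. A shared person intercept gave essentially none.

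**Step 5: weighting.** With the true dropout weights in the arm-differential settings of Step 1, the mean estimate is −0.005 to 0.003 and type I error is 4.5-7.4%.

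**The case against.** The strongest reply is that material bias needs arm-differential dependence and heavy loss together. The protocol itself calls 20% per visit pessimistic, and observed retention at Visit 2 was close to plan. That stands, and it limits the point. So does the fact that the absence of weights and imputation is inferred from silence.

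A second reply is that naming an exchangeable working correlation would settle the matter. That works on burst averages but not at the session level the SAP specifies (Steps 2 and 3).

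A reader might also infer more than the documents support:
- *That the GEE biases the arm effect outright.* With the same dropout mechanism in both arms it does not, to any useful degree.
- *That dependence on any earlier burst is a problem.* Burst 1 is a covariate.
- *That the SAP claims general validity under MAR.* Its consistency claim is conditional; the gap is that this analysis does not meet the condition.
- *That Grid Memory and Symbol Search are safe because they use likelihood.* That holds only if the burst-level intercepts are correlated across bursts, which the SAP does not say.
- *That Rotation Span breaks a stated MAR assumption.* It is exploratory, and the SAP's wording, "For secondary outcomes, approaches to address missing data will also assume MAR", does not reach it.
- *That a Poisson mean is wrong for a count out of six.* A sandwich variance does not need the Poisson variance to be right, so binomial is a preference.

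The SAP also has a supportive Burst 2 analysis of each task. No earlier post-baseline burst exists there, so domain comparisons at 9 months escape this mechanism.

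**Conclusion.** The point holds in a conditional form. For the longitudinal Color Shapes analysis, the stated MAR assumption is wider than what the named method covers, and this follows from the text alone. The arm and arm-by-time effects can be biased if dropout depends on Burst 2 or 3 scores differently in the two arms.

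The size is negligible with equal mechanisms, small at planned dropout, and material only near 20% loss per visit with arm-differential dependence. The direction then turns on a working correlation that the SAP leaves open. These sizes rest on the assumed odds ratios, error rate and SD, none of which is in the documents.

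The outcome is secondary. The primary ANCOVA with multiple imputation and the supportive Burst 2 task analyses are not affected by this mechanism.

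**What to change.** Amend the SAP's secondary analysis of Color Shapes to one of the following:
- **Imputation before the GEE.** Extend the existing MICE approach to Bursts 3 and 4, with prior-burst scores as predictors. MICE here works on burst summaries, so this version is simplest at burst level.
- **Inverse-probability-of-dropout weights.** Model dropout on arm, prior-burst scores and their interaction. This keeps the session-level covariates.
- **A count or binomial mixed model** with person effects explicitly correlated across bursts.

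In addition:
- State that the burst-level intercepts in Model 1 are correlated across bursts. Independent intercepts would give Grid Memory and Symbol Search the same problem.
- State the GEE's working correlation and data level.
- Make the missing-data sensitivity analysis firm rather than optional.
- Keep the unweighted GEE as supportive.
- Treat the exploratory Rotation Span GEE the same way if wanted.

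The cost is SAP wording and a little more analysis work, plus a marginalisation step if the mixed model is chosen. No data collection changes.

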11.2	Informed Consent Forms
	44
11.3	Participant Confidentiality
	44
11.4	Study Discontinuation
	45
12 ETHICAL CONSIDERATIONS	45
13 COMMITTEES	46
14 PUBLICATION OF RESEARCH FINDINGS.....	46
15 REFERENCES	46
16 APPENDIX (Informed consent, study forms).....	52

PRECIS

Study Title: Multicultural Healthy Diet to Reduce Cognitive Decline & Alzheimer's Disease Risk

Objectives: This pilot study is designed to investigate whether consuming a healthy diet that is based on the Dietary Inflammatory Index (DII) and tailored to a multicultural cohort hereafter known as the Multicultural Healthy Diet (MHD) can be adapted for a multicultural middle aged (40-65 yr) middle income cohort in Bronx, New York and whether it improves cognition compared to consuming a usual diet. We propose this study in a middle-aged population because early indicators of cognitive aging may manifest long before old age and because lifestyle factors, such as diet, may have their largest impact during this age period.

The primary objectives are:

1. Show that the MHD can be adapted for a diverse middle-aged cohort in the Bronx.
2. Test whether a MHD intervention can benefit cognitive function in a middle-aged population.
3. Identify components of the MHD associated with stable or improved measures of cognition.

The secondary objective of this pilot is to provide a necessary foundation for understanding how lifestyle interventions (such as the MHD) during midlife impacts clinical endpoints at older ages.

Design and Outcomes

The proposed study **design** is a two-arm randomized clinical trial. Participants in the experimental intervention arm will be exposed to an intervention over an 18 month period (four in-person visits in small groups with the interventionist over a two month intensive phase & monthly telephone coaching starting in month 3 of the intervention till month 18). Assessment visit cover a 27month period (run-in, baseline, months 9 & 18 and 27) at the Aging Research Center (Van Etten Building) at the Albert Einstein College of Medicine (Einstein).

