Assess cognitive domains known to be sensitive to normative cognitive aging and risk for ADRD including visuospatial working memory, short-term associative memory “binding”, and processing speed, using real-time ambulatory assessments over a 7-day period every 9 months to evaluate the time course over which positive impacts are detectable. We also assess inflammatory markers C-reactive protein & IL-6 as possible mechanisms of action. We hypothesize that participants randomized to the MHD diet will have more stable and possibly improved cognitive function relative to baseline, whereas comparison participants will have measurable decline.

A3. Identify components of the MHD associated with stable or improved measures of cognition.

Evaluate biomarkers indicative of a MHD diet pattern (see A1) and relate to cognitive function measures.

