2.2.3 Feasibility- Preliminary Studies

Measurement Burst Design: Feasibility and Participant Compliance:

Dietary patterns and cognition: Preliminary findings from tests of global cognitive function from the Hispanic Community Health Study/Study of Latinos (HCHS/SOL) (n=8,829, 45-74 yrs of age), a cohort that includes participants from Co-op City, Bronx, indicated in a model including age, ethnicity, sex, income and energy intake, the Alternative Healthy Eating Index (AHEI- a diet quality score that assesses the degree to which the diet adheres to the US Dietary Guidelines, was significantly associated with tests assessing verbal episodic learning and memory: the Spanish English Verbal Learning Test (SEVLT) 3 trials and SEVLT Recall. A 10 unit increase in

AHEI-2010 was associated with significant increase in these cognitive scores ($\beta= 0.49$, 95% CI: 0.18, 0.80, $P=0.002$), ($\beta= 0.21$, 95% CI 0.06, 0.36, $P=0.005$) respectively.

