
In-Clinic Cognitive Assessments: Participants will also perform computer based versions of the dot-memory, symbol search and memory binding tasks, to provide us with a point of comparison

for other studies of dietary effects on cognitive function. Other in-clinic cognitive tests include the Stroop Test for processing speed (done visits 1-4 -see descriptor) and tests from the NIH Tool Box (<https://www.nia.nih.gov/research/resource/nih-toolbox>) that will be done at visits 1 & 4- these tests were discontinued during the pandemic as of 3/12/20:

Toolbox Flanker (executive function attention)

Toolbox Picture Vocabulary (language)

Toolbox Dimensional Card sort (EF-judgment/flexibility)

Toolbox Pattern Comparison (processing speed)

WMS Episodic Memory (WMS paired associates)

These tests are accompanied by participant complaints questionnaire used in the Einstein Aging Study at visit 1 (see form) at visit 1 (baseline) and the 6 item Promis v1.0-Applied Cognition-General Concerns-Short Form 6a in follow-up visits.

The Wide Range Achievement Test (WRAT) literacy test will be given once at run-in. *In-Clinic Questionnaires*: Participants will also be asked to complete questionnaires regarding past medical history, concomitant medication, socio-demographic information, education, income, marital status, alcohol, physical activity, smoking and drug use including smoking. APOE4 allele, the gene for apolipoprotein E which is a risk factor for AD will also be assessed. These questionnaires are based on ESCAPE study and have acceptable participant burden drawing on participants from Co-op City (see Appendix and Table 1 in Scott et al., 2015 (66).

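### The exploratory diet-component models that serve objective A3 name no adjustment for ethnicity, income or energy intake, so their associations are open to residual confounding

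*SAP*

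**What the plan says.** The Protocol Precis lists as its third primary objective: "Identify components of the MHD associated with stable or improved measures of cognition". Section 1.1 (A3) describes the work as "Evaluate biomarkers indicative of a MHD diet pattern (see A1) and relate to cognitive function measures" and gives no covariates.

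The SAP takes this up in one paragraph of Exploratory Analyses. The step runs only if an important diet effect on cognition has been found. It is meant "for the dietary components that seem to be the most different between arms at Burst 2", and relates the Burst 2 measure, or its change from baseline, to change in cognition "using models similar to that for the primary analysis of the intervention effect". Formal mediation analyses, and methods that combine biomarker and self-reported intake, are optional extras with no confounders listed.

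In the SAP's Analysis of the Primary Outcome, the arm effect is "adjusted for the baseline Burst 1 composite score measure and stratification variables", the latter being sex, age and years of education. The stated reason for including them is correct confidence interval width under stratified randomisation.

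Protocol Section 2.2.3 reports a preliminary diet-cognition association from an external cohort (n=8,829), estimated "in a model including age, ethnicity, sex, income and energy intake".

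**The concern.** Arm is randomised, so a short covariate list is enough for the primary contrast. An achieved carotenoid level or fruit intake at Burst 2 is not randomised. If arm stays in the model, as it would in a model like the primary one, the component coefficient comes from differences between people within an arm. People who reach higher levels may also differ in income, ethnicity, energy intake, smoking, activity or BMI. Any of these that also bears on nine-month cognitive change could lead to a component being named because of who eats it.

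The SAP lists about 30 self-reported dietary variables as well as the plasma biomarkers. With no confounder set fixed in advance, covariates could also be chosen after the results are seen.

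**Working it through.** The plan states no figure for this analysis, so the check is a comparison of covariate sets, followed by an illustration of size on assumed inputs.

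**1. Term-by-term comparison**

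| Term | Preliminary model (Protocol 2.2.3) | Primary ANCOVA (SAP) |
|---|---|---|
| Age | yes | yes |
| Sex | yes | yes |
| Ethnicity | yes | no |
| Income | yes | no |
| Energy intake | yes | no |
| Baseline cognition | not listed | yes |
| Arm | not applicable | yes |
| Years of education | not listed | yes |

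Each model has five terms and two are shared. Three of the five preliminary adjusters are absent from the model that the component analysis is to resemble.

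**2. Does other SAP text fill the gap?**

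- Adjustment for APOE4, race and ethnicity is a supportive step for Models 1 and 2, which estimate the treatment effect on the individual tasks.
- Adjustment for energy, BMI, race and ethnicity (Analysis of Secondary Outcomes; Missing data approach for the secondary outcomes) is written for diet as the outcome.
- Cholesterol adjustment of carotenoids and tocopherols is likewise written for these biomarkers as outcomes. It is not repeated where they become exposures.

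None of these is written for the component models.

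**3. Are the variables available?** Yes. The in-clinic questionnaires (Protocol Section 3) cover "socio-demographic information, education, income, marital status, alcohol, physical activity, smoking". BMI comes from measured height and weight, ASA24 supplies total calories, and the SAP already uses race and ethnicity elsewhere.

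**4. Illustration of size (assumed inputs)**

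Let one omitted confounder have partial correlation a with the component and b with Burst 2 cognition, given the model's covariates, and let the component have no true effect.

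- Induced partial correlation: r = a × b.
- Shift of the test statistic: m = atanh(r) × √(n − 3 − 5), with five covariates. Here n = 250, the nine-month number in Protocol 9.2, so the multiplier is √242 = 15.56.
- Two-sided rejection at an assumed 0.05: Φ(m − 1.96) + Φ(−m − 1.96).

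| a | b | r | m | False-positive rate |
|---|---|---|---|---|
| 0.1 | 0.1 | 0.01 | 0.16 | 5.3% |
| 0.2 | 0.2 | 0.04 | 0.62 | 9.5% |
| 0.2 | 0.3 | 0.06 | 0.93 | 15.4% |
| 0.3 | 0.3 | 0.09 | 1.40 | 28.9% |

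**5. How demanding are these inputs?** Protocol 9.2 gives a burst-to-burst correlation of about 0.90 and a detectable difference in change of 0.16. The two agree: 0.35 × √(2 × (1 − 0.90)) = 0.35 × 0.447 = 0.157. On that scale the SD of cognition after conditioning on baseline is √(1 − 0.90²) = 0.436. One SD of the confounder then shifts cognition by b × 0.436:

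- b = 0.1: 0.044, or 27% of 0.16
- b = 0.2: 0.087, or 54% of 0.16
- b = 0.3: 0.131, or 82% of 0.16

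The upper rows therefore need a single omitted covariate with a large effect on nine-month change.

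**The case against.** The strongest reply is that the model already conditions on baseline cognition, which the preliminary model does not list. With a burst-to-burst correlation near 0.90, stable traits such as income or ethnicity can confound mainly through a link to nine-month change. This stands. It makes the larger false-positive rates unlikely, but it does not cover factors that affect change itself.

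A second reply is that the analysis is labelled exploratory, runs only after an important diet effect is found and carries no declared error control. Protocol 9.4 also classes diet-cognition associations as exploratory, and A3 itself speaks only of association. This stands too and limits the stakes. It does not remove the value of a stated confounder set for what the Protocol calls a primary objective.

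A reader might infer that the planned model has fewer covariates than the preliminary one. It does not: the count is five against five, and the sets differ in content. A reader might also infer that the SAP restricts adjustment to the primary covariates. The word similar leaves the list open, so the fault is that no further confounders are named.

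Finally, adding covariates carelessly could do harm. BMI or weight at Burst 2 is post-randomisation, and the same SAP section treats weight loss as a possible mediator, so adjusting for it could remove part of the pathway being explored. This is right, and it shapes the fix.

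**Conclusion.** The point holds in a limited form. The SAP's only treatment of A3 relates non-randomised component levels to cognition with a covariate set built for the randomised comparison. It names none of ethnicity, income or energy intake, although the Protocol's own diet-cognition model used all three and the data are collected. The associations are open to residual confounding.

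It would go too far to say that they are confounded, because the documents give neither the size nor the direction of any bias. The 5.3% to 28.9% range rests on one omitted confounder, assumed partial correlations of 0.1 to 0.3, n=250 and a two-sided 0.05 test. Its low end is close to nominal and its high end needs strong assumptions. Nothing here touches the primary between-arm analysis.

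**What to change.** For the exploratory component analysis only, add a confounder-adjusted model to the SAP:

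- Keep baseline composite, arm, age, sex and years of education.
- Add race/ethnicity, income, baseline BMI, baseline smoking and baseline physical activity.
- Add energy intake when the exposure is a self-reported (ASA24) component other than total calories itself, and state which burst's recalls supply it.
- Carry over the SAP's cholesterol adjustment when plasma carotenoids or tocopherols are the exposure.
- Do not adjust for post-randomisation BMI or weight.

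Report the currently planned model beside it, so that the effect of the added terms is visible, and describe the results as associations.

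The cost is SAP wording, about 6 to 9 degrees of freedom out of about 250 depending on how race/ethnicity and smoking are coded, and some loss of cases where covariates are missing. No new data are needed and the primary analysis does not change.
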